3.4 Secondary Endpoints

The study’s secondary endpoints reflect within-subject acute and longitudinal improvements of MDS-UPDRS score from tasks specific to action tremor and BF-ADL score from pre-stimulation to post-stimulation at Visits 2b and 3, captured as defined in the protocol. The statistical objective of the secondary endpoint is to demonstrate, using clinician-rated and patient rated measures, that action hand tremor severity in PD is reduced after treatment with the Cala Trio device.

For purposes of the secondary endpoint:

- ***MDS-UPDRS score*** is defined as the ***average of UPDRS ratings from the two assessed action tremor tasks (postural hold and kinetic) relevant to the stimulated upper limb.***
Observations where either of these two assessments are missing will not be included in the analysis set.

- **BF-ADL score** is defined as the *average of available BF-ADL ratings from the eight assessed tasks (use a spoon to drink soup, hold a cup of tea, pour milk from a bottle or carton, dial a telephone, pick up your change in a shop, insert an electric plug into a socket, unlock your front door with the key, write a letter) relevant to the stimulated upper limb*. For observations where ratings for a subset of these tasks are missing, the BF-ADL ratings from the remaining tasks will be averaged and the observation will still be eligible for inclusion in the analysis set. This was done because missing data are assumed to result from participants not having the necessary props readily available (i.e., data are “missing at random”) and not because participants were systematically unable to perform the respective ADL task.

The secondary endpoints are:

- 1a. Improvement in the MDS-UPDRS score from pre-stimulation to post-stimulation at Visit 2b.
- 1b. Improvement in the MDS-UPDRS score from pre-stimulation to post-stimulation at Visit 3.
- 1c. Improvement in BF-ADL score from pre-stimulation to post-stimulation at Visit 2b.
- 1d. Improvement in BF-ADL score from pre-stimulation to post-stimulation at Visit 3.
- 2a. Improvement in the MDS-UPDRS score from Visit 2b pre-stimulation to Visit 3 post-stimulation.
- 2b. Improvement in BF-ADL score from Visit 2b pre-stimulation to Visit 3 post-stimulation.
- 3a. Improvement in the MDS-UPDRS score from Visit 2b pre-stimulation to Visit 3 pre-stimulation.
- 3b. Improvement in BF-ADL score from Visit 2b pre-stimulation to Visit 3 pre-stimulation.

The secondary endpoints will be summarized descriptively using mean, standard deviation, median, first and third quartiles, and interquartile range (between first and third quartiles). Hypothesis testing of the mean change score (μ_T) will be performed using one-sample t-tests (equivalent to a two-sample paired test). Formally, the null and alternative hypotheses to be tested for each of the secondary endpoints are as follows:

$$H_0: \mu_T = 0$$

$$H_A: \mu_T \neq 0.$$

Secondary endpoints will only be tested for statistical significance if the primary endpoint is met. Secondary endpoints will be tested in a hierarchical stepwise manner, using a fixed sequence procedure: 1a -1d first, 2a and 2b second, and 3a and 3b third. Statistical significance level will be set at $p < 0.05$ for each of the three endpoint groups, with group 2 (2a, 2b) only tested if all tests in group 1 (1a – 1d) meet significance, and group 3 (3a, 3b) only tested if group 2 meets significance. Because all endpoints within a step (e.g., endpoints 1a – 1d in endpoint group 1) must meet the two-sided $p < 0.05$ in order to proceed to the next step, no adjustment for multiplicity is required.

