Once a subject has received the device kit, device training will occur via telemedicine, as follows:

Positioning and Fastening Cala Trio

Prior to device positioning, subjects should dampen the wrist of the prescribed hand to ensure good connection between the electrodes and wrist. Subjects should position the device on the prescribed hand such that the electrodes are positioned over the median and radial nerves, and securely tighten the band.

Device Calibration

To calibrate the Cala Trio device, subjects will perform a series of postural hold tremor tasks, in which the device measures the subject's tremor frequency and sets the stimulation burst frequency based on the measured tremor frequency.

For the purposes of this study, only the outstretched postural hold tremor task will be used.

Setting Stimulation Intensity

The subject will set the stimulation intensity to an amount they can comfortably tolerate while doing light activities. Paresthesia should be perceived in the parts of the hand and/or fingers innervated by the median and radial nerves. The stimulation intensity selected during the initial amplitude calibration is saved on the device for subsequent sessions. The subject can decrease or turn off the stimulation at any point in time and may adjust their stimulation intensity from session to session to maintain the minimum paresthesia threshold.

Device Training

During the course of the visit, study personnel will instruct the subject on proper use of the device. Subjects must demonstrate competence to operate the device and comprehension of the instructions for use prior to completing the training.

Visit 2b

Once a subject is trained on the device, the subject will receive a single 40-minute therapy session with their Cala Trio. The subject will be asked to not stimulate at least 8 hours prior to this visit. The following assessments will be made prior to the therapy session and again immediately post the therapy session:

- Tremor assessments (while in the *off* state) including:
 - Modified MDS Unified Parkinson's Disease Rating Scale Part III (MDS-UPDRS) will be rated by the PI
 - Bain & Findley Activities of Daily Living (BF-ADL) upper limb subset score will be rated by the subject. The BF-ADL assessment will be performed using the subject's own household props

- CGI-S, I/PGI-S, I

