3.2 Analysis Populations

As stated in section 2.2, available data on all enrolled subjects will be summarized and reported, referred to in ICH E9 (“Statistical Principles for Clinical Trials”) as the *full analysis set*.

Two analysis populations will be defined, one consisting of all available data evaluated under intent-to-treat (ITT) principles, and the other consisting of all available data evaluated under per-protocol (PP) principles. Both populations are defined in further detail below. For each analysis population, “available data” means that missing data will not be replaced or imputed, and that endpoints defined as change scores will require both baseline and follow-up data to be present to be included in analyses.

The ITT population consists of all enrolled subjects.

The PP population is defined as ITT subjects who furthermore:

- Met all inclusion/exclusion criteria (in particular, subjects enrolled but determined post-enrollment not to have met one or more eligibility criteria will be excluded from the PP population).
- Were dispensed a stimulator at the primary timepoint (visit 2b) that had been appropriately calibrated to the subject’s tremor; subjects who were dispensed stimulators at the time of visit 2b that had not been calibrated to that subject’s tremor will be excluded from the PP population.
- Remained on a stable dosage of tremor and antidepressant medications, if applicable, during the duration of the study.
- Were rated by a certified UPDRS rater at the primary timepoints (Visit 1, Visit 2b and Visit 3).

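### A BF-ADL change score can compare different tasks at its two time points; take the change over tasks rated at both

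*SAP*

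**What the plan says.** SAP 3.4 defines the BF-ADL score, one observation at a time, as the "average of available BF-ADL ratings from the eight assessed tasks". Where some tasks have no rating, "the BF-ADL ratings from the remaining tasks will be averaged and the observation will still be eligible for inclusion in the analysis set". No minimum number of tasks is set. The reason given is that "missing data are assumed to result from participants not having the necessary props readily available", and not that subjects were systematically unable to do the task. SAP 2.1 explains where the props come from: "The BF-ADL assessment will be performed using the subject's own household props".

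Four of the eight secondary endpoints are differences between two such scores. Two fall within a visit: 1c ("Improvement in BF-ADL score from pre-stimulation to post-stimulation at Visit 2b") and 1d, its counterpart at Visit 3. Two run across visits: 2b ("Improvement in BF-ADL score from Visit 2b pre-stimulation to Visit 3 post-stimulation") and 3b, which ends at the Visit 3 score taken before stimulation. Each is tested with a one-sample t-test on the mean change, two-sided at 0.05. SAP 3.9 adds an exploratory percentage of subjects whose BF-ADL average improves by at least 0.5 points within a visit.

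The UPDRS rule in the same section is stricter: "Observations where either of these two assessments are missing will not be included in the analysis set".

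**The concern.** Subtracting two averages isolates a change in tremor only if both cover the same tasks. If a task is rated at one time point and not at the other, the difference also contains the gap between that task's rating and the rest. UPDRS pairs are protected because incomplete observations are dropped. BF-ADL pairs are not.

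No other section closes the gap. SAP 3.2 says that "endpoints defined as change scores will require both baseline and follow-up data to be present to be included in analyses", but this pairs endpoints, not tasks, and an average over fewer tasks satisfies it. SAP 3.12 promises best-case and worst-case sensitivity analyses only for calculations that impute, and this one does not.

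At stake are the four BF-ADL endpoints and the exploratory responder percentage. Endpoints 1c and 1d also belong to the first group in the testing sequence, all of which must pass before groups 2 and 3 are tested. A task mismatch in the unfavourable direction could therefore stop the sequence, so the sponsor has an interest in the repair too.

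**Working it through.** The documents give no power, rate or variance for the BF-ADL endpoints, so there is no figure of the plan's own to reproduce.

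**Inputs from the documents:** eight tasks; available-task averaging; two-sided 0.05; the 0.5-point responder threshold (SAP 3.9); 34 to 50 subjects (SAP 3.6, stated for the primary endpoint and used here only as a range of N).

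**Assumed inputs, not in the documents:** ratings from 1 to 4 with higher worse, the spread between tasks, and the skip rates.

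**One subject, no rating changed.** If k of 8 tasks are rated before and skipped after:

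recorded improvement = (k/8) × (mean of skipped tasks − mean of kept tasks)

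| Pattern | Before | After | Recorded improvement | On common tasks |
|---|---|---|---|---|
| Seven tasks at 2, one at 4; the 4 skipped after | 18/8 = 2.25 | 14/7 = 2.00 | +0.25 | 0 |
| Six at 2, two at 4; both 4s skipped after | 20/8 = 2.50 | 12/6 = 2.00 | +0.50 | 0 |
| Seven at 2, one at 4; the 4 skipped before only | 14/7 = 2.00 | 18/8 = 2.25 | −0.25 | 0 |
| One at 1, six at 2, one at 4; the 1 skipped after | 17/8 = 2.125 | 16/7 = 2.286 | −0.16 | 0 |
| Seven at 2; the eighth task missing both times | 2.00 | 2.00 | 0 | 0 |

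With one of eight tasks skipped after, a gap of 1, 2 or 3 points gives 0.125, 0.25 or 0.375. The second row reaches the 0.5-point responder threshold without any change in tremor.

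**Group mean.** If a fraction q of subjects skip one task after only, and it lies g points above the others, the mean false gain is q × g/8. With g = 1 this is 0.0125, 0.025 and 0.0375 for q = 10%, 20% and 30%.

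**Effect on the test, hardest task skipped after only.** Simulation of the one-sample t-test with no true change, 3,000 runs per cell:

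| Skipping | Mean change, N = 34 / 50 | Two-sided rejection, N = 34 / 50 |
|---|---|---|
| Hardest task, after only, 10% of subjects | 0.012 / 0.013 | 5.5% / 6.1% |
| Same, 20% | 0.025 / 0.025 | 7.7% / 10.6% |
| Same, 30% | 0.037 / 0.038 | 13.5% / 18.0% |
| Random task, after only, 30% | 0.001 / 0.001 | 5.1% / 5.3% |
| Hardest task, equally often before and after, 30% in total | 0.002 / 0.002 | 5.5% / 5.3% |

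The simulated means agree with q × g/8 at g = 1. At 20% and 30%, nearly all rejections favour the device. Differencing on common tasks gave a mean change of about 0 and rejection of 4.4% to 5.5% in every cell.

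**Effect on the test, missing tasks at both time points.** With N = 45, 10% of tasks missing before, and one to three hard tasks missing more often afterwards, the favourable rejection rate (nominal 2.5%) was:

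- 15% of hard tasks missing after: about 4-9%
- 20%: about 5-19%
- 30%: about 9-60%

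Common-task differencing stayed at about 2.5%. The width of these ranges comes from how many tasks are hard and how hard they are, neither of which the documents give.

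**The case against.** The strongest reply is that the SAP states why tasks go missing. If props are absent for reasons unrelated to difficulty, or equally often at both time points, the mean change is unbiased and the test keeps its level, as the last two simulation rows show. Within a visit, the two ratings bracket one 40-minute session, and Protocol 3.5 describes the telemedicine ADL assessment as supervised, so the same props should usually be to hand. SAP 3.9 already lists per-task BF-ADL changes at Visits 2b and 3. Secondary testing also waits for the primary endpoint, and 2b and 3b are reached only if all of 1a to 1d succeed, including two UPDRS endpoints with complete task sets. The responder percentage is exploratory.

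Most of this stands and limits the reach of the point. It does not close it. The per-task changes are exploratory and cover only within-visit comparisons, so they do not check 2b or 3b. The props assumption is untested, and household props can differ between visits about four weeks apart. Calling the data missing at random is also not enough. If the chance of skipping a task later depends on its observed earlier rating, the data are still missing at random in the statistical sense, yet the difference of available-task averages is biased.

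A reader might infer that the rule favours the device in general, or that subjects skip hard tasks after stimulation. The documents support neither. The direction depends on which side the gap falls, and no section reports or predicts such skipping.

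**Conclusion.** The definition allows a BF-ADL change to mix task difficulty with tremor, and the single-subject arithmetic is exact: 0.25 points for one hard task, in either direction. Bias in the group mean needs two conditions together: skipping related to difficulty, and skipping unequal between the two time points. The SAP's props assumption makes this less likely without ruling it out. Exposure is greatest for 2b and 3b, and smaller for 1c and 1d.

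The size cannot be settled from the documents. Under the stated assumptions the favourable false-positive rate per endpoint runs from close to nominal to about 60%. A reader might be tempted to quote one figure from inside that range as the error rate of the plan, but it would mainly reflect the chosen skip rate and task spread. These are also per-endpoint rates, not trial-level ones, because of the testing sequence. The change is worth making because it is cheap and removes the task-mix artefact whatever the skip rate.

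**What to change.** In SAP 3.4, define the BF-ADL change for 1c, 1d, 2b and 3b as the mean of task-level differences over the tasks rated at both time points of that comparison. Apply the same rule to the exploratory 0.5-point BF-ADL responder percentage in SAP 3.9. Keep the available-task version as a sensitivity analysis.

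The cost is one sentence, and partly complete observations stay in, as the SAP intends. There are three downsides:

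- The task set can differ between comparisons.
- A subject with no common task drops out of that comparison.
- Bias remains if skipping depends on the later rating itself. In one assumed case (30% of tasks that would score 4 skipped, 5% of others), the false gain fell from 0.043 to 0.019 but did not vanish.

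Tabulating missing tasks by visit and time point, with the reason (no prop or unable), would show whether the props assumption holds.

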3 STATISTICAL METHODS

3.1 General Principles

- All hypothesis testing will be performed using a two-sided test at a 0.05 level of significance or a one-sided test at a 0.025 level of significance. Significance levels will be adjusted for multiple hypothesis testing where appropriate. P-values will be reported as raw uncorrected p-values and rounded to three decimal places. If a p-value is less than 0.001 it will be reported as “< 0.001.”
- Summary statistics will be reported for all analyzed variables.
 - Continuous data will be summarized using descriptive statistics appropriate for the underlying data distribution, e.g., mean, standard deviation, median, and interquartile range (first and third quartiles).
 - Categorical, non-ordered variables will be summarized using frequency counts and percentages.
 - Ordinal variables, including those specific to study outcomes – e.g., the modified Movement Disorder Society Unified Parkinson’s Disease Rating Scale (MDS-UPDRS) Part III and the Bain & Findley Activities of Daily Living (BF-ADL) scale – will be summarized using measures of central tendency and variance as opposed to frequency counts and percentages; that is, these variables will be reported using the same metrics as defined above for continuous variables.
- For events which can occur more than once in a single subject (e.g., adverse events), the percentage will be based on number of subjects experiencing the event, and both subject and event counts will be reported.
- Baseline is defined as the last measurement for the outcome of interest obtained before the exposure to study treatment.
- For time-to-event analyses, complete dates for events of interest (e.g., index treatment, outcome events, censoring), will always be used. Incomplete dates will be incorporated by defining the event as occurring on the earliest date possible given the incomplete information. E.g., a date of UNK-FEB-2018 will be incorporated into the analysis as 01-FEB-2018.
- Statistical analyses will be performed in SAS (SAS Institute, Cary, N.C.) version 9.3 or later, R (R Foundation for Statistical Computing, Vienna, Austria) version 3.2 or later,

Matlab (The MathWorks, Inc., Natick, MA) version R2016B or later, Python (Anaconda, Inc., Austin, TX) version 3.6.6 or later, or in another validated statistical software package.

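### SAP 3.4's reason for no multiplicity adjustment protects secondary groups claimed as a whole, but not a single endpoint claimed from a partly passed group, which the SAP does not bar

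*SAP*

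**What the plan says.** SAP 3.4 defines eight secondary endpoints. Group 1 (1a to 1d) is the change from before to after stimulation on MDS-UPDRS and BF-ADL at Visits 2b and 3. Group 2 (2a, 2b) runs from Visit 2b pre-stimulation to Visit 3 post-stimulation. Group 3 (3a, 3b) runs from Visit 2b pre-stimulation to Visit 3 pre-stimulation. Testing starts only if the primary endpoint is met.

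Some of the wording attaches significance to the group. The 0.05 level is set "for each of the three endpoint groups", and the last gate reads "group 3 (3a, 3b) only tested if group 2 meets significance".

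Other wording attaches it to the single endpoint. The section introduces its two-sided hypotheses with "the null and alternative hypotheses to be tested for each of the secondary endpoints are as follows", gives each endpoint its own one-sample t-test, and makes group 2 "only tested if all tests in group 1" are significant.

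The reason for not adjusting is that every endpoint in a step must reach two-sided p < 0.05 "in order to proceed to the next step, no adjustment for multiplicity is required".

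SAP 3.1 adds two general rules: "Significance levels will be adjusted for multiple hypothesis testing where appropriate" and "P-values will be reported as raw uncorrected p-values and rounded to three decimal places".

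**The concern.** The stated reason is a rule for moving between groups. It settles when group 2 or group 3 may be tested, but not what may be claimed inside a group where some endpoints pass and others fail. In group 3 the reason has no force at all, because no step follows.

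SAP 3.1 does not close this gap. It names no method and leaves adjustment to judgement, and SAP 3.4 then declares that none is needed here. A report that called 1a significant after 1c had failed would break no written rule.

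This matters because the secondary endpoints are meant to carry a conclusion: "The statistical objective of the secondary endpoint is to demonstrate, using clinician-rated and patient rated measures", that action tremor is reduced. Raw p-values would make a mixed result visible, but the SAP has no rule for what could then be claimed.

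**Working it through.** **Inputs.** From SAP 3.4: groups of 4, 2 and 2 endpoints; two-sided 0.05 per endpoint (0.025 in the direction of improvement); all endpoints in a group must pass before the next is tested. The documents give neither the correlation between endpoints nor the power for secondary endpoints. Assumed: equal correlations of 0 to 0.9 and, for mixed results, power of 80% to 90% per endpoint. All error rates below take the primary endpoint as met.

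**1. The SAP's own statement, groups claimed whole.** Take the first group in the sequence that contains a true null. A false claim there or later requires that null to be rejected, so the chance is at most 0.05 two-sided over the whole sequence. The worst case is one null endpoint beside large true effects. Simulated with four t-tests, n = 45 and correlation 0.5, it gives 0.0501, of which 0.0245 is false improvement. The statement is therefore correct for whole-group claims. The corresponding bound for false improvement is 2.5% at non-negative correlations.

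**2. Single claims, all nulls in the group true, independent endpoints.**
- Group 1, improvement: 1 − 0.975^4 = 0.096; two-sided: 1 − 0.95^4 = 0.185.
- Two-endpoint group, improvement: 1 − 0.975^2 = 0.049; two-sided: 1 − 0.95^2 = 0.0975.

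**3. The same with correlation** (equicorrelated normal statistics, limit 1.96, simulated).

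| Chance of at least one false claim | corr. 0 | corr. 0.5 | corr. 0.9 |
|---|---|---|---|
| Group 1, improvement (nominal 2.5%) | 9.6% | 7.8% | 4.7% |
| Group 1, two-sided (nominal 5%) | 18.5% | 15.6% | 9.4% |
| Group 3 if reached, improvement | 4.9% | 4.5% | 3.5% |

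Simulated t-tests at n = 34 and n = 50, the ends of the SAP 3.6 range, give 9.6%, 7.8% to 7.9% and 4.8% for the first row.

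**4. Why group 2 differs.** For subjects with complete data, the definitions in SAP 3.4 give change 2a = change 1b + change 3a, and change 2b = change 1d + change 3b. Group 2 is reached only after 1b and 1d have passed. If those are real improvements, both group 2 nulls can be true only if pre-stimulation scores worsened over four weeks by exactly the offsetting amount on both scales. If they are not real, group 2 is almost never reached. The two-endpoint figures are therefore realistic for group 3 but describe a nearly unreachable state for group 2.

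**5. How often group 1 would pass only in part.** If all four endpoints are independent with 80% power: 1 − 0.8^4 − 0.2^4 = 1 − 0.4096 − 0.0016 = 0.59. With 90% power: 1 − 0.6561 − 0.0001 = 0.34. At correlation 0.9 these fall to 0.18 and 0.11, so the range is 11% to 59%. If MDS-UPDRS responds with 80% to 90% power and BF-ADL does not respond, the range is 87% to 99%.

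**The case against.** The strongest reply is that the defect is only a silence. The level is set per group, the method is described as a stepwise fixed sequence, and group 2 is spoken of as reaching significance as a unit. Read that way, per-endpoint p < 0.05 is simply what a group needs in order to pass, no adjustment is required, and no sentence permits a claim from a failed group. This largely stands. A reader might infer that the procedure is invalid or that its error rate is 18.5%. The documents do not support that: the figure applies only if single claims are made, all four group 1 nulls are true and the endpoints are independent. What remains is that the whole-group reading is not written as a claim rule, while separate hypotheses and separate tests are.

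It can also be said that strict error control adds little to secondary endpoints in a single-arm, unblinded study (SAP 2.1; Protocol 3.7) whose ratings come from the investigator and the subjects, and that raw p-values expose a mixed result. That is a fair reason to rank the point low. It does not supply the missing rule.

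Finally, comparing 9.6% with the whole-group rate when every null is true (below 0.1% for group 1 if independent) would flatter the criticism. The fair comparison is the whole-group worst case of 2.5% for improvement, or 5% two-sided.

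**Conclusion.** The point holds in a limited form and is minor. The no-adjustment statement is correct for whole-group claims. It does not control error for a single endpoint claimed from a partly passed group, and the SAP does not rule such claims out. The exposure is a 4.7% to 9.6% chance of at least one false improvement claim in group 1, and 3.5% to 4.9% in group 3 if reached, against 2.5%. These figures rest on assumed correlations of 0 to 0.9, a met primary endpoint and all nulls in the group being true.

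Two further inferences should be resisted. Group 2 is not exposed in the same way as group 3, because its changes are sums of group 1 and group 3 changes. Nor is the trial's main conclusion touched: SAP 3.3 makes study success depend on the primary endpoint alone.

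**What to change.** Replace the no-adjustment sentence in SAP 3.4 with one of two rules.

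(a) *No endpoint in a group will be claimed as statistically significant unless every endpoint in that group has two-sided p < 0.05 in the direction of improvement; otherwise its p-values are descriptive. Because each group is claimed only as a whole and in fixed order, no adjustment is required.* Direction is needed because the alternatives are two-sided, so a significantly worsened endpoint would otherwise count as a pass. The cost is real: every claim from a mixed group is lost, which on the assumptions above could happen for group 1 in 11% to 59% of trials even when all four endpoints respond.

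(b) If single-endpoint claims are wanted, apply Hochberg within each group at two-sided 0.05, claim only improvements, and go on only if all endpoints in the group are rejected in the direction of improvement. This keeps the present p < 0.05 gate: four p-values of 0.04 still pass, because the largest is below 0.05. It assumes positive dependence between the endpoints. Holm avoids that assumption but tightens the gate: the smallest of four p-values of 0.04 is compared with 0.05/4 = 0.0125, each adjusted value is 4 × 0.04 = 0.16, and testing stops.

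Either rule is a short change of SAP wording, with no change to data collection or the primary test.
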